Medical resource utilization	Information on all health care needs during treatment (eg, physiotherapist) to be collected	Continuous from the time of signing of the ICF until 30 days after the last dose of study drug			
Patient-reported outcomes					
FACT-Leu	PROs should be performed on Day 1 of each cycle before dosing and before any study tests or procedures are conducted.		X	X	Only at first FU
EQ-5D-5L			X	X	Only at first FU
Laboratory Assessments					
Hematology	At least the following parameters (hemoglobin, platelet count, absolute WBC count, absolute monocyte count, absolute basophil count, absolute eosinophil count, absolute neutrophil count, absolute lymphocyte count, and peripheral blast count) must be assessed within 3 days of the indicated days of each cycle and results reviewed prior to starting dosing if applicable.	X	Days 1, 8, and 22	X	
Coagulation panel	aPTT, INR or prothrombin time (PT) must be assessed at screening and as clinically indicated afterward	X			
Clinical chemistry	At least the following parameters (AST, ALT, sodium, potassium, magnesium, BUN, phosphate, uric acid, calcium, alkaline phosphatase, creatinine, total bilirubin) must be assessed within 3 days of Day 1 of each cycle and results reviewed prior to starting the cycle.	X	X	X	
Assessment for active hepatitis or history of HIV		X			
Serum β -hCG or urine pregnancy test	For women of childbearing potential only	X	Only if clinically indicated		

Procedure (Part B)	Notes	Screening Phase	Open-Label Treatment Phase		Follow-up Phase
		Within 28 days before randomization	Day 1 of each cycle (± 48 hours) unless otherwise indicated (each cycle = 28 days)	EOT	Every 3 months (±7 days)
Disease Evaluations: A +/- 7-day window exists for completion of disease evaluation visits. Refer to Section 9.2 for details on efficacy evaluations					

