Infusion-related reaction	6 (100)	2 (66.7)	3 (50.0)	0	5 (55.6)	16 (59.3)
Headache	4 (66.7)	1 (33.3)	3 (50.0)	1 (33.3)	2 (22.2)	11 (40.7)
AML Recurrent	1 (16.7)	2 (66.7)	1 (16.7)	0	4 (44.4)	8 (29.6)
Fatigue	1 (16.7)	2 (66.7)	2 (33.3)	0	2 (22.2)	7 (25.9)
Nausea	2 (33.3)	1 (33.3)	3 (50.0)	0	0	6 (22.2)
Chills	0	0	2 (33.3)	1 (33.3)	2 (22.2)	5 (18.5)
Dizziness	1 (16.7)	1 (33.3)	0	0	3 (33.3)	5 (18.5)
Pyrexia	0	0	1 (16.7)	0	3 (33.3)	4 (14.8)
Arthralgia	1 (16.7)	0	2 (33.3)	0	1 (11.1)	4 (14.8)
Hypotension	1 (16.7)	0	1 (16.7)	2 (66.7)	0	4 (14.8)
Vomiting	2 (33.3)	1 (33.3)	1 (16.7)	0	0	4 (14.8)
Diarrhea	0	0	2 (33.3)	0	2 (22.2)	4 (14.8)
Hypertension	2 (33.3)	0	1 (16.7)	0	0	3 (11.1)
Tachycardia	2 (33.3)	0	1 (16.7)	0	0	3 (11.1)
Constipation	0	1 (33.3)	1 (16.7)	0	1 (11.1)	3 (11.1)
Contusion	1 (16.7)	0	0	0	2 (22.2)	3 (11.1)
CRP Increased	0	0	1 (16.7)	1 (33.3)	1 (11.1)	3 (11.1)
Neuropathy peripheral	0	0	0	0	2 (22.2)	2 (7.4)
Chest discomfort	0	1 (33.3)	1 (16.7)	0	0	2 (7.4)
Chest pain	0	0	2 (33.3)	0	0	2 (7.4)
Oedema peripheral	0	1 (33.3)	0	0	1 (11.1)	2 (7.4)
Blood urea increased	0	0	1 (16.7)	1 (33.3)	0	2 (7.4)
Neutrophil count decreased	0	1 (33.3)	0	0	1(11.1)	2 (7.4)
Hyperglycaemia	1 (16.7)	0	0	1 (33.3)	0	2 (7.4)
Hypokalaemia	0	0	1(16.7)	1 (3.3)	0	2 (7.4)
Hypomagnesaemia	0	0	2 (33.3)	0	0	2 (7.4)
Nasopharyngitis	0	0	0	1 (33.3)	1 (11.1)	2 (7.4)
Upper respiratory tract infection	0	1 (33.3)	0	0	1 (11.1)	2 (7.4)
Urinary tract infection	0	0	1 (16.7)	0	1 (11.1)	2 (7.4)
Pain in extremity	0	1 (33.3)	0	0	1 (11.1)	2 (7.4)
Cough	0	0	0	1 (33.3)	1 (11.1)	2 (7.4)
Hypoxia	0	0	2 (33.3)	0	0	2 (7.4)
Thrombocytopenia	0	0	0	0	2 (22.2)	2 (7.4)

Data cutoff date: 28 January 2015

Source: CSLCT-AML-11-73 Interim report

The majority of adverse events were Common Terminology Criteria for Adverse Events (CTCAE) Grade 1 or 2. Four subjects were reported with Grade 3 adverse events related to treatment with CSL362. One subject from the 0.3 mg/kg cohort was reported with Grade 3 hypertension. The remaining subjects with drug-related adverse events were from the 1.0 mg/kg cohort. One subject was reported with Grade 3 pyrexia, another subject was reported with Grade

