6.3.2. Talacotuzumab: Premedication

All subjects receiving talacotuzumab in the current study must receive premedication during the first 4 cycles, as outlined in Table 5. If no infusion-related reactions, independent of severity, are seen for 2 consecutive cycles during the first 4 cycles of talacotuzumab treatment, then premedication may be modified per investigator discretion after discussion with the Sponsor for

Cycle 5 and subsequent talacotuzumab treatments. In the event an infusion-related reaction (independent of severity) occurs in subsequent talacotuzumab treatments, premedication needs to be reintroduced. If a subject has a medical condition or clinical need that precludes complete administration of premedications at any time, notification to and discussion with the Sponsor's study physician is required.

Table 5: Premedication for Subjects Receiving Talacotuzumab

Part A and Part B – Arm 1	Infusion-related Reaction	Mandatory Premedication ²
Cycle 1- Cycle 4		
Dexamethasone 8 mg PO (or equivalent) twice per day approx. 2 days prior to infusion and approx. 3 hrs prior to infusion
 
Methylprednisolone (100 mg IV)¹ approx. 1-2 hrs prior to infusion
 
Acetaminophen (paracetamol) 650 – 1000 mg IV or PO approx.1 hr prior to infusion
 
Antihistamines: diphenhydramine 25 – 50 mg IV or PO³ and cimetidine 300 mg PO (or equivalent⁴) approx. 1 hr prior to infusion
 
Leukotriene inhibitor (montelukast 10 mg PO, or equivalent), approx. 1-2 hrs prior to infusion

Cycle 5 + Subsequent cycles	If Prior Event:	
Dexamethasone 8 mg PO (or equivalent) twice per day approx. 2 days prior to infusion and approx. 3 hrs prior to infusion
 
Methylprednisolone (100 mg IV)¹ approx. 1-2 hrs prior to infusion
 
Acetaminophen (paracetamol) 650 – 1000 mg IV or PO approx.1 hr prior to infusion
 
Antihistamines: diphenhydramine 25 – 50 mg IV or PO³ and cimetidine 300 mg PO (or equivalent⁴) approx. 1 hr prior to infusion
 
Leukotriene inhibitor (montelukast 10 mg PO, or equivalent), approx. 1-2 hrs prior to infusion

	No Prior Event for 2 consecutive cycles:	Premedication may be modified per investigator discretion and after discussion with the Sponsor

¹ If methylprednisolone is not available at the institution, consult with Sponsor regarding corticosteroid selection.

Dose and frequency may be increased at the discretion of the investigator.

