Blood samples for serum chemistry and hematology will be collected as specified in the [Time and Events Schedule Tables 1A and 1B and 1C](#). Additional clinical laboratory tests may be performed as indicated by the overall clinical condition of the subject or if abnormalities warrant more frequent monitoring. Hematology and serum chemistry laboratory evaluations may be repeated as clinically indicated. The investigator must review the laboratory results, document this review, and record any clinically relevant changes occurring during the study in the adverse event section of the eCRF. The laboratory reports must be filed with the source documents. Screening laboratory results must be available to the investigator for evaluation before the first dose of study drug on Day 1 of Cycle 1.

The following tests will be performed by the local laboratory:

- Hematology Panel
 - hemoglobin
 - absolute white blood cell (WBC) count
 - platelet count
 - absolute monocyte count
 - absolute basophil count

- absolute eosinophil count
- absolute neutrophil count
- absolute lymphocyte count
- peripheral blast count
- Coagulation:
 - activated partial thromboplastin time (aPTT)
 - International normalized ratio (INR) or prothrombin time (PT)
- Serum Chemistry Panel

-sodium	-aspartate aminotransferase (AST)
-potassium	-alanine aminotransferase (ALT)
-magnesium	-alkaline phosphatase
-creatinine	-calcium
-total bilirubin	-blood urea nitrogen (BUN)
-phosphate	-uric acid
- Serum β -hCG or urine pregnancy testing for women of childbearing potential only (screening only) or if clinically indicated or required by local regulations.

Electrocardiogram (ECG)

Electrocardiogram will be performed for all subjects during screening as indicated in the [Time and Events Tables 1A](#) and [1B](#). Abnormalities noted at screening should be included in the medical history. During the collection of ECGs, subjects should be in a quiet setting without distractions (eg, television, cell phones). Subjects should rest in a supine position for at least 5 minutes before ECG collection and should refrain from talking or moving arms or legs. If blood sampling or vital sign measurement is scheduled for the same time point as ECG recording, then the procedures should be performed in the following order: ECG(s), vital signs, blood draw.

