6.8.2. Clinical Laboratory Tests

Selected hematologic and chemistry laboratory parameters will be descriptively summarized at each scheduled on-treatment evaluation by treatment group. Change from baseline will also be summarized. Mean value over time will be presented graphically.

A summary of the shifts in selected laboratory hematology and serum chemistry parameters from baseline to the worst toxicity grade during the study (from treatment start to 30 days after last dose or the end of treatment visit date, whichever is later) will be provided.

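### Glucose is not a scheduled test in Part B although high-dose steroid premedication is mandatory in the combination arm only, so hyperglycaemia is not systematically measured and its between-arm comparison is unreliable

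*Protocol*

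**What the plan says.** **Required chemistry.** Table 1B (Part B, in force up to and including Amendment 5) schedules chemistry at screening, on Day 1 of each cycle and at end of treatment. The row opens "At least the following parameters (AST, ALT, sodium, potassium, magnesium", so it is a minimum list, and it continues through 12 analytes: "AST, ALT, sodium, potassium, magnesium, BUN, phosphate, uric acid, calcium, alkaline phosphatase, creatinine, total bilirubin) must be assessed within 3 days of Day 1". Protocol Section 9.9 repeats the same 12 under "Serum Chemistry Panel". The Part A list in Table 1A has no glucose either, so this is not a slip in one table. Section 9.9 also permits extra testing: "Additional clinical laboratory tests may be performed as indicated by the overall clinical condition of the subject".

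**Days 8 and 22.** Hematology is the only routine safety panel that Table 1B schedules on these days, with a 3-day window.

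**Steroids.** Protocol Section 6.3.2, Table 5, requires for Cycles 1 to 4 "Dexamethasone 8 mg PO (or equivalent) twice per day approx. 2 days prior to infusion and approx. 3 hrs prior to infusion", plus "Methylprednisolone (100 mg IV", the latter one to two hours beforehand. From Cycle 5 the same cover applies after a prior reaction. It may be modified if two consecutive cycles passed without one. Only Arm 1 receives talacotuzumab.

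**Analysis.** SAP Section 6.8.2 summarises selected parameters at scheduled on-treatment evaluations and adds "A summary of the shifts in selected laboratory hematology and serum chemistry parameters from baseline to the worst toxicity grade". Hyperglycaemia is not among the adverse events of special interest in SAP Section 5.16.

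**The concern.** Premedication is part of the randomised regimen, and its complexity was one of the reasons given when benefit/risk was judged unfavourable (Protocol Section 3.1). A rise in blood glucose is a foreseeable effect of corticosteroids, exposure to them differs between arms by design, and Part B enrols subjects aged 65 or over. If no glucose value is scheduled, the safety tables cannot say how often hyperglycaemia occurred in either arm. A reader of the study report could take a small or absent difference as evidence of no difference.

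**Working it through.** The plan states no figure on this point to reproduce. The check sets the schedules side by side and then asks what can be said about the direction of any bias.

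**1. Scheduled glucose values.** Glucose is on neither Part B list (12 analytes in Table 1B, the same 12 in Section 9.9). The scheduled number is therefore 0 per subject in both arms. That includes baseline: SAP Section 5.5 takes the last value on or before randomization, and screening requires no glucose. A baseline-to-worst-grade shift can be formed only for a subject whose site happened to measure glucose both before and during treatment.

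**2. Steroid occasions against chemistry draws, Cycles 1 to 4.**
- Infusions with unconditional premedication: 4 cycles × 2 (Days 8 and 22) = 8.
- Scheduled Day 1 chemistry draws in the same cycles: 4.

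**3. Distance between draws and steroids on the nominal schedule.**
- Dexamethasone starts about 2 days before the Day 8 infusion, so about Day 6. Gap from the Day 1 draw: 6 − 1 = 5 days, with the draw first.
- From the Day 22 infusion to the next Day 1 (Day 29): 29 − 22 = 7 days.
- With every allowed window stacked (infusion 24 hours late, next cycle 48 hours early, chemistry 3 days before that): (29 − 2 − 3) − (22 + 1) = 24 − 23 = 1 day. This is the extreme case.

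Adding glucose to the existing Day 1 draw alone would therefore usually miss the days on which the steroids act.

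**4. The hematology draws on Days 8 and 22.** With the 3-day window, the Day 8 sample may be taken on 8 − 3 = Day 5 and the Day 22 sample on 22 − 3 = Day 19. Dexamethasone starts at about Days 6 and 20. A glucose value carried on those draws could precede the steroid unless the draw is fixed to the infusion day.

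**5. Direction of bias.** Let p₁ and p₀ be the true incidences (combination, decitabine alone) and s₁ and s₀ the shares detected.
- Recorded incidence in each arm is s·p, which is at most p. It is too low whenever detection is incomplete.
- Recorded ratio = (s₁/s₀) × (p₁/p₀). It is unchanged if detection is equal, and inflated if the steroid arm is checked more closely.
- True minus recorded difference = (1 − s₁)p₁ − (1 − s₀)p₀. The difference is understated if more cases per subject are missed in the combination arm, overstated if more are missed in the control arm, and unchanged if the two are equal.

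The documents give none of p₁, p₀, s₁ or s₀, so the sign cannot be settled.

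**The case against.** **There is a back-up, and it stands.** The list is a minimum and indicated tests are allowed. Laboratory abnormalities are adverse events by definition (Protocol Section 12.1.1). Concomitant therapies are recorded in both arms, and SAP Section 6.8.1 tabulates adverse events by preferred term, grade and arm. The accurate statement is that hyperglycaemia is not systematically measured, rather than that it is never measured.

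**Tilt towards the combination.** A reader might infer that the gap flatters the combination arm. The documents do not support this. The laboratory tables hold no scheduled glucose comparison to tilt. For adverse events the trial is open label (Protocol Section 5), so closer checking of the steroid arm could enlarge the contrast as easily as missed cases could shrink it.

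**Cumulative steroid exposure.** A reader might multiply the current Table 5 doses by eight infusions and call the result what the arm received. The amendment log rules that out for nearly everyone. Dexamethasone entered with Amendment 3 and its present schedule with Amendment 5 (26 April 2017), and Amendment 6 (2 August 2017) stopped talacotuzumab. Those two issue dates are 98 days apart, and Cycle 1 Day 8 to Cycle 4 Day 22 also spans 3 × 28 + 14 = 98 days. Earlier subjects had lighter cover. Short low-dose steroid courses are also permitted in either arm (Protocol Section 8.1).

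**The Phase 1 cases.** Table 1 of the protocol lists "Hyperglycaemia" in 2 of 27 subjects, and a reader might take this as a steroid signal. One case was at 0.3 mg/kg, a cohort without hydrocortisone premedication, and there were 0 of 9 at 9 mg/kg. It is not evidence of a steroid effect.

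**Timing.** Table 1C, which replaced Table 1B, schedules no laboratory tests, and talacotuzumab has stopped. This limits what can still be changed but does not supply the missing data.

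**Conclusion.** The gap is real and moderate. Followed as written, Part B yields no scheduled glucose value in either arm, while the mandatory steroid cover falls in one arm only. The incidence of hyperglycaemia is probably under-recorded, and the between-arm comparison is unreliable in an undetermined direction. The size of the error cannot be estimated from the documents. The conclusion rests on two assumptions: that corticosteroids can raise blood glucose, which is general pharmacology and not a figure in the plan, and that local or indicated testing does not find every case. Nothing here touches CR, OS, alpha or power, or the decision to stop talacotuzumab.

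**What to change.** **Design form.** Add glucose to the chemistry lists in Table 1B and Protocol Section 9.9, with a screening value. Schedule it in both arms on Day 1 and on Days 8 and 22 themselves: before the infusion in Arm 1, on matched days in Arm 2, and without the 3-day window. Name glucose among the SAP Section 6.8.2 shift-table parameters. The cost is one routine local-laboratory analyte at visits where blood is already drawn, less flexibility in timing that draw, and more low-grade abnormalities to record. A pre-infusion sample follows the start of dexamethasone but may not show the full effect of the methylprednisolone.

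**What can still be done.** Because Table 1B applies only up to Amendment 5 and talacotuzumab has been stopped, the usable change is in the SAP:
- In Section 6.8.2, state that glucose was not a scheduled analyte, so that its absence from the laboratory tables is not read as absence of the event.
- In Section 6.8.1, tabulate hyperglycaemia adverse events by arm and grade.
- In Section 6.4, report by arm the glucose-lowering drugs newly started on or after the first dose. The planned coding by ATC class already supports this, but a start-date condition is needed because SAP Section 5.8 also counts drugs continued from before treatment as concomitant.
- Attach the ascertainment caveat to both tables: unscheduled detection, open label, direction of bias unknown.

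This uses data already collected and costs a few lines of SAP text and two tables.

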1. INTRODUCTION

Acute myeloid leukemia (AML) is a heterogeneous disease characterized by uncontrolled clonal expansion of hematopoietic progenitor cells.²⁶ As the second most common form of leukemia, AML accounts for the largest number of annual deaths from leukemia. This poor prognosis is in part due to the fact that AML affects patients at a more advanced median age of 67 years with a third of patients diagnosed at an age of over 75 years.^{26,28} Advanced age associated with comorbidities, concomitant end-organ dysfunction, and poor performance status severely limits tolerance to cytotoxic chemotherapy. In addition, the biology of AML in the elderly also contributes to the poor therapeutic outcome. In older patients, AML arises more frequently from an overt or unrecognized myelodysplastic syndrome (MDS), and appears to be associated with complex, monosomal, or combination karyotypes, adverse cytogenetics, as well as a multidrug resistant phenotype.²⁵ Although these patients may respond to chemotherapy, increased drug-related deaths offset clinical benefit.²⁰ As a consequence, major therapeutic advances associated with intensification of chemotherapies and the broader availability of curative allogeneic stem cell transplantation have primarily benefited the smaller subpopulation of younger AML patients. In contrast, the choice of more effective treatment options for the majority of elderly patients has remained very limited. In recent years, the hypomethylating agent decitabine (formulated product, DACOGEN[®]) has emerged as one of the preferred therapies for AML patients who cannot tolerate intense induction and consolidation chemotherapy.^{5,25} Decitabine promotes cellular differentiation by reversing epigenetic suppression of gene expression, thus inducing durable responses in a subset of patients with AML. In a Phase 3 study, DACOGEN demonstrated a higher rate of complete responses (CRs) compared to the standard of care therapy of low-dose cytarabine (17.8% versus 7.8%).²¹ Given the well described and predictable safety profile, multiple clinical studies are currently underway to improve the efficacy of decitabine in AML patients in novel combination regimens.

In this Phase 2/3 study, the safety and clinical efficacy of a combination of decitabine with the novel, therapeutic antibody talacotuzumab, directed against the α -subunit of the interleukine-3 receptor (CD123) overexpressed on leukemic blasts and leukemic stem cells (LSCs), will be explored in patients with previously untreated AML who are not eligible for intense induction chemotherapy.

For the most comprehensive nonclinical and clinical information regarding talacotuzumab and decitabine, refer to the latest version of the Investigator's Brochure and Addenda.^{15,16} The term "sponsor" used throughout this document refers to the entities listed in the Contact Information page(s), which will be provided as a separate document.

1.1. Talacotuzumab (JNJ-56022473; CSL362): Second Generation Anti-CD123 Antibody

Acute myeloid leukemia is a disorder of early hematopoietic progenitor cells, characterized by the proliferation and accumulation of immature, clonal, myeloid cells. Constitutive overexpression of the α -subunit of the interleukin-3 receptor ie, IL-3R α , is a hallmark of the early AML progenitor cell population (ie, leukemic stem cells) as well as leukemic blasts. CD123 is unique to the IL-3 receptor and is responsible for the high specificity and low affinity binding of IL-3. Upon ligand binding, the α -subunit CD123 associates with the β_c -subunit (CD131) to form a high-affinity receptor complex initiating an intracellular signaling cascade through phosphorylation and activation of at least 3 distinct signal transduction pathways: the JAK/STAT-kinase, MAP-kinase-, and PI3-kinase-pathways. Under physiological conditions, activation of the IL-3 receptor induces proliferative, anti-apoptotic, and differentiating signals.¹²

Talacotuzumab (JNJ-56022473; CSL362) is a second generation antibody developed from the murine 7G3 anti-CD123 monoclonal antibody (mAb) in a stepwise process of humanization, affinity maturation, and Fc engineering. To enhance the cytotoxicity of the first-generation antibody CSL360, the proprietary Xencor (Xmab[®]) technology was applied and two amino acid mutations (S239D and I332E) were introduced into the Fc region.¹⁶ These amino acid substitutions led to improved binding to CD16 (Fc γ RIIIa) on natural killer (NK) cells and significantly enhanced the ability to induce antibody-dependent cell-mediated cytotoxicity (ADCC).³

The talacotuzumab drug product that will be used in this study is produced in a different cell line with a different process compared with CSL362, the drug product used in the Phase 1 study CSLCT-AML-11-73 described below. Comparability testing of talacotuzumab and CSL362 has shown the antibodies to behave similarly in biophysical, biochemical, and preclinical assessments. The primary structure, charge heterogeneity, size heterogeneity, purity, higher order structure, and process impurities were found to be highly similar between CSL-362 and talacotuzumab. Pharmacodynamic (PD) studies in cynomolgus monkeys showed similar levels of biological activity between CSL362 and talacotuzumab (ie, basophil and pDC depletion; NK cell number and activity). Additionally, the PK profiles of talacotuzumab following 30 and 100 mg/kg IV dosing of cynomolgus monkeys are highly similar to those of CSL362. Following the first weekly IV dose, mean C_{max} and AUC_{0-167h} of talacotuzumab are 91% and 94% of those observed for CSL362, respectively.

